 - Systemic corticosteroids (at doses over the equivalent of 1 mg prednisone daily); inhaled, intranasal or topical corticosteroids are acceptable
 - PC-SPES
 - Saw Palmetto
 - Megestrol
 - Ketoconazole
 - 5- α -reductase inhibitors – patients already taking 5- α -reductase inhibitors prior to 28 days prior to registration may stay on these agents throughout the course of therapy, but these should not be started while patients are on study
 - Diethyl stilbesterol
 - Abiraterone
 - Any other hormonal agent or supplement being used with the intent of cancer treatment

6. External beam radiation therapy within 4 weeks of registration is prohibited, or anticipated need for radiation therapy (e.g. imminent pathological fracture or spinal cord compression) within 3 months of registration.
7. Major surgery within 4 weeks of registration is prohibited
8. Prior cytotoxic chemotherapy (e.g. docetaxel, mitoxantrone, cabazitaxel) within 6 months of registration is prohibited
9. Patients with a history of life-threatening autoimmune disease
10. Patients who have undergone splenectomy
11. Patients must not have other active malignancies other than non-melanoma skin cancers or carcinoma in situ of the bladder. Subjects with a history of other cancers who have been adequately treated and have been recurrence-free for ≥ 3 years are eligible.
12. Patients with known brain metastases
13. Any antibiotic therapy or evidence of infection within 1 week of registration
14. Any other medical intervention or condition, which, in the opinion of the PI could compromise patient safety or adherence with the study requirements
15. Patients cannot have concurrent enrollment on other phase I, II, or III investigational treatment studies.

6. **Experimental Design**

This will be a 1:1 randomized, open-label, single institution pilot trial designed to evaluate the immunological and clinical effect of booster immunizations with a DNA vaccine encoding PAP with rhGM-CSF adjuvant following treatment with sipuleucel-T. Study arms will be defined as follows:

- Arm 1: sipuleucel-T – administered intravenously (i.v.) per standard of care biweekly, weeks 0, 2, and 4
- Arm 2: sipuleucel-T – administered intravenously (i.v.) per standard of care biweekly, weeks 0, 2, and 4

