An immune response will be defined based on the detection of augmented numbers of PAP-specific effector (IFN γ -secreting and/or granzyme B-secreting) and/or memory (proliferating) T-cell immune response after immunization, using blood obtained at 6 months for the primary analysis compared with pre-treatment. Specifically, a positive antigen-specific response resulting from immunization will be defined as a PAP-specific response by two or more of these three tests detectable at the 6-month post-treatment time point that is significantly ($p < 0.05$, two-sided using a two-sample t-test) higher than to media only, at least 3-fold higher than the mean baseline value, and with a frequency > 10 per 10^6 PBMC, based on 8-well replicate assays (for ELISPOT-based assays) or triplicate assays (for proliferation analysis). Otherwise, a patient will be declared as an immune non-responder.

Immune response will be determined as a static time point at 6 months, and “durable” immune responses will also be determined by the presence of a PAP-specific immune response by the criteria above detectable at 3, 9, or 12 months after study entry.

C.2. Secondary Clinical and Immunological Endpoints

C.2.1. Time to Progression

Time to progression will be defined as a function of baseline time points in two ways:

- (1) *Time to progression from randomization*: Time elapsed from randomization until disease progression or death. If a patient doesn't experience a disease progression or death event before the end of the follow-up period, then the observation for this patient will be censored.
- (2) *Time to progression from 3 months post-randomization*: Time elapsed from the 3 months disease progression assessment until disease progression or death. If a patient doesn't experience a disease progression or death event before the end of the follow-up period, then the observation for this patient will be censored.

The rationale for defining time to progression as a function of baseline time points (date of randomization and 3-month disease assessment) is described in Section 6 (B).

C.2.2. Twelve-month Progression Free Survival Rate

The 12-month progression free survival rate will be defined as the proportion of patients progression free at the 12 month (post-randomization) disease assessment time point.

C.2.3. Overall Survival

Overall survival will be defined as the time interval from randomization to death from any cause or to the last follow-up in censored patients.

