A difference in the immune response rate of 55% between the two arms will be detected with at least 84% power. Analogously, a difference in the efficacy response rate of only 40% between the two arms will be detected with 53% power at the one-sided 5% significance level. In order to account for unevaluable patients, 30 eligible patients (15 per arm) will be accrued and randomized. Based on past experience with this patient population treated at our institution, we anticipate that the proposed total number of 30 patients will be accrued within 18 months. Each patient will be followed for at least 12 months.

G. Statistical Analysis Plan

G.1. General

This section outlines the statistical analysis strategy and procedures for the study. If after the study has begun changes are made to primary and/or key secondary objectives, or the statistical methods related to those objectives, then the protocol will be amended.

Summary tabulations will be presented that will display the number of observations, mean, standard deviation, median, range, minimum, and maximum for continuous variables and the number and percent per category for ordinal and categorical data. All endpoints of this study will be presented graphically where possible using boxplots and histograms for continuous variables and (stacked) bar charts for categorical variables. Data analysis will be performed using SAS[®] (SAS Institute Inc., Cary, North Carolina) version 9.2 or greater.

There are many comparisons made between the two trial arms for multiple measurements, both clinical and laboratory. However, since this a pilot study, no adjustment will be made for

multiple comparisons. Except for the primary immunological endpoint, where the comparison between arms will be conducted at the one-sided 0.05 significance level, all other comparisons will be made using a two-sided test at a significance level of 0.05 without adjustment for multiplicity.

G.2. Baseline Comparability

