The detection of antigen spread to other prostate associated antigens, and the identification of specific antigens recognized, will be analyzed descriptively. In addition, logistic regression analysis will be conducted to evaluate whether antigen spread is associated with the generation

of PAP-specific immune responses elicited as a result of treatment. The dependent variables will be the detection of IgG responses to ≥ 1 “off-target” antigen at 6 months (and not present pre-treatment) while treatment arm and 6-month PAP-specific immune responses (no vs. yes) will be included as covariates. The results will be reported in terms of odds ratios and the corresponding 95% confidence intervals.

13. Administrative Considerations

A. Specimen Handling

Upon entry into the study, each subject will be assigned a unique identification number. All materials collected on that subject will be labeled with that number only, for reasons of confidentiality. Lymphocytes collected will be stored in liquid nitrogen, and sera will be aliquoted and stored at -80°C in the research laboratory of the PI for immune analysis.

B. Institutional Review Board

In accordance with federal regulations (21 CFR 312.66), an Institutional Review Board (IRB) that complies with the regulations in 21 CFR 56 must review and approve this protocol and the informed consent form prior to the initiation of the study at each investigator site. In addition, the study cannot be instituted without FDA approval of the vaccine formulations. Finally, the trial will be conducted with adherence to this protocol, following good clinical practice (GCP) guidelines, and in compliance with other applicable regulatory requirements. Any modifications to the protocol must follow the procedure as outlined in Section 16 below.

C. Consent

The local Principal Investigator, co-investigators, or their associates must explain verbally and in writing the nature, duration, and purpose of the study and possible consequences of the treatment. Patients must also be informed that they may withdraw from the study at any time and for any reason without jeopardizing their future treatment. In accordance with Federal regulations (21 CFR 312), all patients must sign the IRB-approved consent form.

14. Data and Safety Monitoring Plan

A. Oversight and Monitoring Plan

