The UWCCC Data and Safety Monitoring Committee (DSMC) is responsible for monitoring data quality and subject safety for all UWCCC clinical studies. A summary of DSMC activities follows:

- Review of all clinical trials conducted at the UWCCC for data integrity and safety
- Review of all serious adverse events requiring expedited reporting as defined in the protocol
- Review of reports generated by the UWCCC data quality control review process
- Submit recommendations for corrective action to the CRC

- Notify the Local Principal Investigator of the DSMC’s recommendation to the CRC
- Work in conjunction with the Health Sciences IRB in the review of protocol deviations, violations and unanticipated problems reported by the UWCCC DOWGs.
- The committee ensures that notification is provided to all external sites participating in multiple-institutional clinical trials coordinated by the UWCCC of serious adverse events requiring expedited reporting.

Phase II Trials

Data related to these trials are discussed at regularly scheduled Disease Oriented Working Group meetings where the result of each subject’s treatment is discussed and the discussion is documented in the minutes. The discussion will include for each treatment arm/dose level, the number of subjects, significant toxicities as described in the protocol, dose adjustments, and responses observed. Protocol Summary Reports are required for submission to the Data and Safety Monitoring Committee for review.

B. Review and Oversight Requirements

B.1. Serious Adverse Event – Reported Within 24 Hours :

Serious Adverse Events requiring reporting within 24 hours (as described in Table D-2) must also be reported to the Data and Safety Monitoring Committee (DSMC) Chair via an email to [contact] within one business day. A 24 hr. initial “SAE Details” Report, generated in the UWCCC database, must be attached to the email along with any pertinent information available at the time of initial reporting. The DSMC Chair will review the information and determine if immediate action is required. Within 10 working days, all subsequent SAE documentation must be submitted electronically along with a 24 hour follow-up “SAE Details” Report and a completed UWCCC SAE Routing Form to [contact]. All information is entered and tracked in the UWCCC database.

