C. Description of Procedures to Maintain Confidentiality of Research Specimens

All specimens obtained for the immunological evaluation of this trial (blood specimens) will be delivered to the laboratory of [name]. Specimens received by [name] lab will only be handled by laboratory personnel who have undergone HIPAA training and annual UWHC-mandated blood-borne pathogen safety training. Receipt of specimens will be entered into a database that will provide a unique code for each specimen. All stored specimens (sera,

peripheral blood mononuclear cells) will be labeled with this unique code and the date of preparation. Thus, all patient identifiers will be removed from the final stored samples, and any data generated will contain only the unique code as identifier. A database will be maintained to link individual coded specimens with an individual subject (name, hospital medical record number, date/time point) in order to be able to compare information from samples obtained at different time points from a specific individual, and ultimately for transfer of research data to the clinical trials database. This research database will only be available to the study investigators, not other laboratory personnel, to maintain confidentiality. Subject sera will be maintained indefinitely in the laboratory of the study principal investigator, stored in aliquots at -20°C to -80°C . Peripheral blood mononuclear cells will be stored indefinitely in the laboratory of the study principal investigator, stored in aliquots in liquid nitrogen.

D. Modifications of Protocol and Deviations from Protocol

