Subjects are informed during the consenting process, and in the consent form, that their participation is voluntary and they may withdraw consent at any time and for any reason. If subjects wish to withdraw from the study, they will be asked, but not required, to perform the off-study procedures/blood draws. They will be again informed that their decision to participate or not participate at any time will not affect their routine medical care or any other benefits to which they were otherwise entitled. In addition, subjects will be removed from study participation if there is a concern for patient safety, as described above, if they are unable to comply with study procedures, or if the study is terminated by local or national regulatory agencies.

F. Roles and Responsibilities of Study Personnel at UWCCC

Study Principal Investigator:

[name] MD PhD, Associate Professor of Medicine, is a genitourinary medical oncologist, with a clinical research and laboratory interest in immune-based therapies for prostate cancer. He has served as the principal investigator for several other clinical trials, and has had formalized training in the ethics and conduct of clinical trials and human subjects protection. He will be overall responsible for the conduct of the trial and its analysis, but will not participate in patient accrual, treatment of patients on study, or interpretation of clinical data. [name] involvement will center on the scientific aspects of the project, including overall trial design and analysis of samples from the trial. [name] will participate as author on any manuscripts derived from this research.

UWCCC Local Principal Investigator:

[name] MD, Associate Professor of Medicine, is a genitourinary medical oncologist with a primary interest in genitourinary cancer clinical trials research. He will be the UWCCC local principal investigator for this study. As UWCCC local PI he will be responsible for activities involving direct patient care and interaction, including recruitment, consent, clinical care and adverse event reporting. The UWCCC local PI will also assume the role of principal investigator on the protocol and UW HS-IRB submission, working with the UW HS-IRB as the responsible investigator to obtain and maintain UW HS-IRB approval for the study. The UWCCC local PI will also be responsible for reviewing significant adverse events that occur at UWCCC and will oversee the care provided by the UWCCC co-investigators on this study.

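### The open-label trial's primary endpoint is assayed in the PI's laboratory with no stated masking of assay readers to arm or visit; the 16.C coding conceals only in part, and 13.A gives a different label rule

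*Combined protocol and SAP*

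**What the plan says.** **Design and endpoint.** Section 6 states: "This will be a 1:1 randomized, open-label, single institution pilot trial". Under 12.C.1 a responder has a "PAP-specific response by two or more of these three tests detectable at the 6-month post-treatment time point". The three tests are the IFNγ ELISPOT, the granzyme B ELISPOT and T-cell proliferation. Each must exceed media only, reach at least 3-fold the baseline mean and pass a frequency floor. Section 12.G.1 says that for this endpoint "the comparison between arms will be conducted at the one-sided 0.05 significance level".

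**Labels and the link.** Section 13.A stores cells and sera in the PI's research laboratory for immune analysis. Of everything collected from a subject it says: "All materials collected on that subject will be labeled with that number only, for reasons of confidentiality". Section 16.C issues a separate code for each specimen on receipt. Stored specimens "will be labeled with this unique code and the date of preparation", and patient identifiers are removed. A linking database holds name, record number and date or time point. Of it the section says: "This research database will only be available to the study investigators, not other laboratory personnel, to maintain confidentiality".

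**People.** Section 16.F describes the study PI's involvement as "including overall trial design and analysis of samples from the trial". The same paragraph keeps the PI out of accrual, treatment and interpretation of clinical data. Section 16.B keeps immune results in laboratory charts for each subject and assigns analysis of immunological response data to the study statistician.

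**Assays.** Section 10.A allows fresh assays, batched cryopreserved assays, or both. Section 10.A.1 uses thawed cryopreserved cells and an automatic plate reader for ELISPOT. Section 10.A.2 estimates proliferation by flow cytometry and ModFit.

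**The concern.** The primary comparison rests on laboratory values that set each patient's month-6 sample against his own baseline sample. Treatment is known to staff and patients, so the comparison is protected only if those who produce the values do not know which arm and visit a sample comes from. The plan does not say that they do not know.

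The protection it does give was written for privacy. It leaves the link with study investigators, a group that on an ordinary reading includes the PI who is responsible for sample analysis. It also leaves a date on the tube.

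If knowledge of arm or visit affected a proliferation fit, or a decision to rerun or discard a plate, the effect could favour the hypothesis. With 14 evaluable patients per arm, a few calls decide the result. Even if no influence occurred, a positive result could not be defended against the suggestion.

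**Working it through.** **1. Sections side by side**

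| Question | 13.A | 16.C |
|---|---|---|
| Code on the tube | Subject number | Unique to the specimen |
| Other information on the tube | None | Preparation date |
| Who can link to the subject | Not stated | Study investigators |
| Stated purpose | Confidentiality | Confidentiality |

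Neither section mentions masking to arm or visit. Under 13.A the tube identifies the patient, whose arm is known in an open-label trial. Under 16.C the date gives the order of samples. A sample assayed fresh reveals its approximate visit whatever its label says.

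**2. Where judgement can enter**

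- ELISPOT counts: little, because a machine counts the spots.
- Responder criteria: little, because they are numeric.
- Proliferation: gating and the ModFit estimate.
- Fresh or batched assay: left open in 10.A.
- Repeating or rejecting a run: no rule is stated for the three primary tests.

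Because two of three tests must be positive, changing one test changes the patient's call only when exactly one of the other two is positive. A changed proliferation result therefore matters only when exactly one ELISPOT is positive.

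**3. Checking the method against the plan's own power table**

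Inputs from 12.F: 14 evaluable per arm, 25% vs 75%, one-sided 5%. With x1 and x2 responders in Arms 1 and 2, the unstratified exact p-value is P(X ≥ x2), where X is hypergeometric: 14 drawn from 28, of whom x1 + x2 are responders. Power is the sum over all 15 × 15 tables of Bin(x1; 14, p1) × Bin(x2; 14, p2) wherever p ≤ 0.05.

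This reproduces 15 of the 16 cells of Table 12.2 within 1 percentage point. The exception is the design cell: 75.2% against the stated 80% (75.4% to 75.6% when stratified with 7 and 7, or 10 and 4, patients per arm in the two strata). That difference is a separate matter and does not affect what follows.

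**4. One changed patient-level call**

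- 5/14 vs 10/14: sum over k = 10 to 14 of C(14,k)·C(14,15−k), divided by C(28,15) = 2,402,778 / 37,442,160 = 0.064.
- 4/14 vs 10/14: sum over k = 10 to 14 of C(14,k)·C(14,14−k), divided by C(28,14) = 1,142,975 / 40,116,600 = 0.028.
- 4/14 vs 9/14: p = 0.064, so one upgraded Arm 2 call also leads to 0.028.
- Further from the boundary, 4/14 vs 11/14 gives p = 0.011. Losing one Arm 2 responder gives 4/14 vs 10/14, which is still significant.

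**5. How often a trial is one call from the boundary**

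| True rates | Significant | Not significant, but one favourable call away |
|---|---|---|
| 25% vs 75% | 75.2% | 11.3% |
| 25% vs 25% | 2.0% | 5.5% |

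With the strata sizes used in step 3, the 11.3% becomes 11.6% to 11.8%. At 25% vs 75%, a further 15.2% of trials are significant but would lose significance after one adverse call.

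Under no difference, type I error is 2.0%. It becomes 4.4% if one Arm 2 non-responder is always upgraded. It becomes 7.6% (2.03% + 5.55%) if the single most helpful change in either arm is chosen after the results are seen. The last figure is a worst case, not an estimate of bias.

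**The case against.** The plan contains more protection than a quick reading suggests, and most of it stands.

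- **Concealment exists.** Section 16.C removes identifiers and closes the link to bench staff other than study investigators. Arm is not among the listed contents of the link. A reader might infer that the laboratory works with arm and visit in plain view; the documents do not show that.
- **Discretion is limited.** ELISPOT is machine-counted, the thresholds are fixed, two of three tests must be positive, and the statistician analyses the response data. A reader might infer that nothing else guards an open-label endpoint, or that any single influenced reading could turn the trial. Neither follows.
- **The PI is separated from patients.** Section 16.F excludes the PI from accrual and treatment, and does not say that the PI reads assays in person.
- **The meetings prove little.** Section 14.A says of working-group meetings: "The discussion will include for each treatment arm/dose level, the number of subjects". This is general institutional text. It does not establish that assay readers attend, and the attendee names in 16.B have been removed from the public document.
- **The label conflict may be one of sequence.** Section 13.A could describe labels at collection and 16.C labels after receipt. In any case the differing rules do not create the risk of bias; the missing masking rule does.
- **Small exact tests are always sensitive near the boundary.** At the design rates, 5/14 vs 10/14 itself arises in only about 3.2% of trials.

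What survives is that confidentiality coding with the link held by investigators and a date on the tube is not reader masking, and that some analytical choices remain open.

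**Conclusion.** The point holds as a cheap improvement. The plan specifies no masking of assay readers, and the coding that it does specify is incomplete. It is not shown that any reader will know arm or visit, or that any call will be influenced.

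The possible effect is confined to results near the boundary. At 25% vs 75%, about 11% of trials would gain significance from one favourable patient-level call. This rests on 14 evaluable patients per arm, the plan's assumed rates and an unstratified exact one-sided test; stratifying changes it little. The documents do not give the number of borderline calls, so no bias can be estimated. A reader might take the p-values as evidence of bias; they show only how little would be needed at the boundary.

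**What to change.** 1. Replace the label rules in 13.A and 16.C with one rule: tubes at the assay bench carry a random specimen code only, with no subject number, arm, visit or date.
2. Give the link to subject, arm and visit to the study biostatistician, who already generates the randomization list (16.A).
3. For the primary endpoint, run each patient's baseline and month-6 cryopreserved samples in the same batch, so that visit can be masked. Section 10.A.1 already describes cryopreserved cells for ELISPOT, so the main change is to proliferation. Samples assayed fresh can be masked to arm only and would be supportive for this endpoint.
4. Lock ELISPOT counts, gating, ModFit fits and every decision to repeat or reject a run before the link is opened. The biostatistician then computes the responder call from the locked values.

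**Cost.** Protocol wording and a code list. The biostatistician must supply sample pairs and run a lock step. Enough cells must be frozen at both visits, whereas 10.A now freezes only what is left after direct use. Sample size, significance level and visits do not change.
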